## 6.5. Follow-up

The F/U visit should occur 40 days (+ 7 days) days after the last administration of DS-8201a. If the subject begins another anticancer therapy before the end of the 40 days (+ 7 days), every effort will be made to complete all the F/U assessments prior to commencing the new therapy. In case of unresolved AEs, including significant abnormal clinical laboratory values at the end of study assessment, these events will be followed until resolution or until they become clinically not relevant. If assessments at EOT or treatment period are performed within this period, they can be considered to be the F/U data and there is no need to repeat them. If discontinuation of treatment is decided later than 40 days after the last administration of DS-8201a, there is no need to perform the F/U assessments.

The following information will be collected at this F/U visit:

- Obtain vital sign measurements (systolic and diastolic blood pressure and pulse rate, respiratory rate and body temperature).
- Perform a complete physical examination and record the subject's weight.
- Assess functional status using the ECOG PS scale (Section 17.3).
- Obtain blood samples for clinical laboratories (Section 8.8) and ADA (Section 7.4.1). For subjects with positive ADA at F/U visit, additional serum ADA samples may be collected every 3 months ( $\pm 1$  month) up to 1 year from the last dose of study drug, or if the ADA becomes negative, or if ADA titer becomes less than Baseline (applicable when pre-existing ADA is observed), or if the subject starts another therapy for cancer, or withdraws consent from the study, whichever occurs first. A portion of ADA blood sample from each subject who provides consent will be used for future central lab analysis for SARS-CoV-2 testing once protocol version 5.0 is applied for a subject. SARS-CoV-2 testing will be conducted every 4 cycles from Cycle 4 (Cycle 4, Cycle 8 etc.).
- Obtain a serum or urine sample for pregnancy testing in women of childbearing potential. For postmenopausal subjects (no childbearing potential, as indicated by an elapse of at least 12 months after the last

menstruation) or female subjects who have no possibility of pregnancy due to sterilization surgery, etc., no pregnancy test will be required. Female subjects who have been amenorrheic for 12 months or longer for medical reasons other than sterilization surgery (eg, effect of medication) will be regarded as women of child-bearing potential and required to undergo the pregnancy test.

- Obtain SpO2.
- Record concomitant medications.
- Assess subjects for AEs.

#### **6.6. New Cancer Treatment and Survival Follow-up**

Not Applicable.

## 7. PHARMACOKINETIC/PHARMACODYNAMIC ASSESSMENTS

### 7.1. Pharmacokinetic Assessments

The PK sampling will be performed at time points indicated in Section 7.1.1.

Detailed instructions on collection, processing, handling, storage, and sample shipment are described in the separate Laboratory Manual.

#### 7.1.1. Serum Sampling

Blood samples for PK will be collected into blood sampling tubes supplied by the Sponsor. The collected blood will be centrifuged to separate the serum. The serum samples will be shipped to a central laboratory.

Instructions for the handling and shipping of serum samples are included in a separate document (eg, laboratory manual)

Blood samples of approximately 7 mL for PK analyses will be collected at the time points specified in Section 17.6 and tabulated in Table 7.1.

The actual time of study drug administration (start and EOI) and the exact time of blood sampling must be recorded in source document and the eCRF. Any delays or interruptions in the infusion of dose should also be recorded.

**Table 7.1: Pharmacokinetic Sampling Time Points**

Cycle	Day	Sampling Time Point (Acceptable Range)
Cycle 1 and Cycle 3	Day 1	Predose (within 8 hours of BI) EOI (within 15 minutes after dose administration) 2 hours after start of administration ( $\pm$ 15 minutes) 4 hours after start of administration ( $\pm$ 15 minutes) 7 hours after start of administration ( $\pm$ 15 minutes)
	Day 2	24 hours after start of administration ( $\pm$ 2 hours)
	Day 4	72 hours after start of administration ( $\pm$ 2 hours)
	Day 8	168 hours after start of administration ( $\pm$ 1 day)
	Day 15	336 hours after start of administration ( $\pm$ 1 day)
	Day 22	504 hours after start of administration ( $\pm$ 2 days), collect only if the next cycle is delayed by 3 or more days, including if the subject cannot continue onto the next cycle, collect blood sample 21 days after the start of administration
Cycle 2, Cycle 4, Cycle 6, and Cycle 8	Day 1	Predose (within 8 hours of BI) EOI (within 15 minutes after EOI)
	Day 22	504 hours after start of administration ( $\pm$ 2 days), collect only if the next cycle is delayed by 3 or more days, including if the subject cannot continue onto the next cycle, collect blood sample 21 days after the start of administration

BI = before infusion; EOI = end of infusion

In case of chloroquine or hydroxychloroquine administration for SARS-CoV-2 infection, additional PK serum samples should be collected at the time points specified in Table 7.2.

**Table 7.2: Schedule of PK Sample Collection for Subjects Administered Chloroquine or Hydroxychloroquine**

Day of CQ or HCQ Administration	Sampling Time Point (Acceptable Ranges)
Day 1	Prior to CQ/HCQ dose
Day 3 or Day 4	Prior to CQ/HCQ dose (within 4 hrs)
End of CQ or HCQ treatment	Prior to CQ/HCQ dose (within 4 hrs)
Prior to resumption of DS-8201a (after CQ/HCQ wash-out period) a	Before infusion of study treatment (within 8 hrs)

CQ = chloroquine; HCQ = hydroxychloroquine.

a Washout period of no less than 14 days is required before resumption of DS-8201a.

## 7.2. Pharmacodynamic Assessment(s)

Not applicable.

## 7.3. Biomarker and Exploratory Assessment(s)

Not applicable.

## 7.4. Immunogenicity

### 7.4.1. Anti-Drug Antibodies

Blood samples for ADA analyses of approximately 4 mL will be collected at the time points specified in [Table 7.3](#). Serum concentrations of DS-8201a and/or total anti-HER2 antibody may be measured using the same ADA samples for the purpose of ADA assessment.

Instructions for the handling and shipping of serum samples are included in a separate document (eg, laboratory manual).

**Table 7.3: ADA Sampling Time Points**

Cycle	Day	Sampling Time Point (Acceptable Range)
Cycle 1	Day 1	BI (within 8 hours before administration)
	Day 8	± 1 day
Cycle 2	Day 1	BI (within 8 hours before administration)
After Cycle 4 at every 2 cycles (eg, Cycle 4, 6, 8, 10, 12, and so on)	Day 1	BI (within 8 hours before administration)
EOT	-	The date investigator decides the discontinuation of the study drug (+ 7 days).
F/U*	-	40 days (+7 days) after the last study drug administration or until starting new anticancer treatment, whichever comes first.

BI = before infusion; EOT = end of treatment; F/U = follow-up; ADA = anti-drug antibodies;

\* For subjects with positive ADA at F/U visit, additional serum ADA samples may be collected every 3 months ( $\pm$  1 month) up to 1 year from the last dose of study drug, or if the ADA becomes negative, or if ADA titer becomes less than Baseline (applicable when pre-existing ADA is observed), or if the subject starts another therapy for cancer, or withdraws consent from the study, whichever occurs first.

#### **7.4.2. SARS-CoV-2 Serum samples collection**

Portion of ADA blood sample from each subject who provides consent will be used for future central lab analysis for SARS-CoV-2 testing once protocol version 5.0 is applied for a subject. Samples will be sent to the central laboratory and stored until the tests will become available.

#### **7.5. Pharmacogenomic Analysis**

Not applicable.

## **8. SAFETY EVALUATION AND REPORTING**

### **8.1. Assessment of Safety Endpoint Event(s)**

Safety endpoints will include SAEs, TEAEs, AEs and AESIs leading to discontinuation, physical examination findings (including ECOG PS), vital sign measurements, standard clinical laboratory parameters, ECG parameters, ECHO or MUGA findings, and ophthalmologic assessments. TEAEs will be graded according to the NCI-CTCAE version 4.03.

### **8.2. Adverse Event Collection and Reporting**

All clinical AEs occurring after the subject signs the ICF and up to the F/U visit after the last dose of study drug (ie, the F/U period) defined as 40 + 7 days, whether observed by the Investigator or reported by the subject, will be recorded on the AE Case Report Form (CRF) page. Medical conditions (including clinical laboratory values/vital signs that are out of range) that were diagnosed or known to exist prior to informed consent will be recorded as part of medical history.

All AEs and SAEs are to be reported according to the procedures in Section 8.5.

All clinical laboratory results, vital sign measurements, and ECG results should be assessed by the Investigator to determine their clinical significance. Isolated abnormal clinical laboratory results, vital signs, or ECG findings (ie, not part of a reported diagnosis) should be reported as AEs if they are symptomatic, lead to study drug discontinuation, dose reduction, require corrective treatment, or constitute an AE in the Investigator's clinical judgment.

At each time point, the Investigator will determine whether any AEs have occurred by evaluating the subject. AEs may be directly observed, reported spontaneously by the subject or by questioning the subject at each time point. Subjects should be questioned in a general way, without asking about the occurrence of any specific symptoms. The Investigator must assess all AEs to determine seriousness, severity, and causality, in accordance with the definitions in Section 8.4. The Investigator's assessment must be clearly documented in the study site's source documentation with the Investigator's signature.

Always report the diagnosis as the AE or SAE term. When a diagnosis is unavailable, report the primary sign or symptom as the AE or SAE term with additional details included in the narrative until the diagnosis becomes available. If the signs and symptoms are distinct and do not suggest a common diagnosis, report them as individual entries of AE or SAE.

For events that are serious due to hospitalization, the reason for hospitalization must be reported as the SAE (diagnosis or symptom requiring hospitalization). A procedure is not an AE or SAE, but the reason for the procedure may be an AE or SAE. Pre-planned (prior to signing the ICF) procedures or treatments requiring hospitalization for pre-existing conditions that do not worsen in severity should not be reported as SAEs (see Section 8.4.2 for Definitions).

For deaths, the underlying or immediate cause of death should always be reported as an SAE.

PD is a study endpoint and consequently, should not be reported as an AE/SAE. However, when a subject dies from PD with no other immediate causes, “Progressive disease” should be reported as an SAE. In addition, any serious, untoward event that may occur subsequent to the reporting period that the Investigator assesses as related to the study drug should also be reported and managed as an SAE. The Investigator should follow subjects with AEs until the event has resolved or the condition has stabilized. In case of unresolved AEs, including significant abnormal clinical laboratory values at the end of study assessment, these events will be followed until resolution or until they become clinically not relevant.

### **8.3. Adverse Events of Special Interest**

For the DS-8201a clinical program, based on the available pre-clinical data, review of the cumulative literature, reported toxicities for the same class of agents and biological plausibility, ILD and LVEF decreases are considered to be AESI.

Additional relevant information regarding the AESIs for the DS-8201a clinical program regardless of seriousness is to be collected through the targeted questionnaires built within the applicable eCRFs in the clinical study database.

For broad surveillance of LVEF decrease, relevant AEs under the MedDRA SMQs of Cardiac Failure is included for enhanced data collection; additional data for these AEs are collected via TQs of heart failure.

For broad surveillance of ILD, selected 42 Preferred Terms (PTs) [all from the ILD Standard MedDRA Query (SMQ)] plus 2 PTs of acute respiratory failure and respiratory failure are included for enhanced data collections.

Please refer to Section 3.2.5 for management of AESIs in this study.

#### **8.3.1. Interstitial Lung Disease Adjudication Committee**

An independent ILD Adjudication Committee for the DS-8201a program is responsible for reviewing all cases of potential ILD/pneumonitis. To ensure adequate and relevant independent evaluation, systematic additional data collection will be conducted for all cases that will be brought for adjudication. These additional data collection will cover a more in-depth relevant medical history (eg smoking, radiation, COPD and other chronic lung conditions), diagnostic evaluation, treatment and outcome of the event. This data collection will be triggered for adverse events reported using selected 42 Preferred Terms [all from the ILD Standard MedDRA Query (SMQ)] plus 2 PTs of acute respiratory failure and respiratory failure.

### **8.4. Adverse Event**

#### **8.4.1. Definition of Adverse Event**

An AE is any untoward medical occurrence in a subject and that does not necessarily have to have a causal relationship with this treatment. An AE can therefore be any unfavorable and unintended sign (including an abnormal clinical laboratory finding, for example), symptom, or disease temporally associated with the use of a medicinal product, whether or not considered related to the medicinal product (International Council for Harmonisation [ICH] E2A Guideline. Clinical Safety Data Management: Definitions and Standards for Expedited Reporting, Oct 1994).

It is the responsibility of investigators, based on their knowledge and experience, to determine those circumstances or abnormal clinical laboratory findings which should be considered AEs.

#### **8.4.2. Serious Adverse Event**

An SAE is any untoward medical occurrence that at any dose:

- Results in death,
- Is life-threatening,
- Requires inpatient hospitalization or prolongation of existing hospitalization,
- Results in persistent or significant disability/incapacity,
- Is a congenital anomaly/birth defect, or
- Is an important medical event.

Note: The term “life-threatening” in the definition of “serious” refers to an event in which the subject was at risk of death at the time of the event; it does not refer to an event which hypothetically might have caused death if it were more severe (ICH E2A Guideline. Clinical Safety Data Management: Definitions and Standards for Expedited Reporting, Oct 1994).

Medical and scientific judgment should be exercised in deciding whether expedited reporting is appropriate in other situations, such as important medical events that may not be immediately life-threatening or result in death or hospitalization but may jeopardize the subject or may require intervention to prevent one of the other outcomes listed in the definition above. Examples include allergic bronchospasm, convulsions, and blood dyscrasias or development of drug dependency or drug abuse.

Note:

- Procedures are not AEs or SAEs, but the reason for the procedure may be an AE or SAE.
- Pre-planned (prior to signing the ICF) procedures or treatments requiring hospitalizations for pre-existing conditions that do not worsen in severity are not SAEs.

#### **8.4.3. Severity Assessment**

All AEs will be graded (1 to 5; see below) according to the NCI-CTCAE version 4.03:

- Grade 1 Mild AE
- Grade 2 Moderate AE
- Grade 3 Severe AE
- Grade 4 Life-threatening consequences; urgent intervention indicated
- Grade 5 Death related to AE

Severity vs. Seriousness: Severity is used to describe the intensity of a specific event while the event itself, however, may be of relatively minor medical significance (such as severe headache). This is not the same as "seriousness," which is based on

patient/event outcome at the time of the event. For example, the NCI-CTCAE Grade 4 (life-threatening consequences; urgent intervention indicated) is assessed based on unique clinical descriptions of severity for each AE, and these criteria may be different from those used for the assessment of AE seriousness. An AE assessed as Grade 4 based on the NCI-CTCAE grades may or may not be assessed as serious based on the seriousness criteria.

#### **8.4.4. Causality Assessment**

The Investigator should assess causal relationship between an AE and the study drug on the basis of his/her clinical judgment and the following definitions. The causality assessment must be made based on the available information and can be updated as new information becomes available.

- Related:
  - The AE follows a reasonable temporal sequence from study drug administration, and cannot be reasonably explained by the subject's clinical state or other factors (eg, disease under study, concurrent diseases, and concomitant medications).

or

- The AE follows a reasonable temporal sequence from study drug administration, and is a known reaction to the drug under study or its chemical group, or is predicted by known pharmacology.
- Unrelated:
  - The AE does not follow a reasonable sequence from study drug administration, or can be reasonably explained by the subject's clinical state or other factors (eg, disease under study, concurrent diseases, and concomitant medications).

#### **8.4.5. Action Taken Regarding Study Drug(s)**

- Dose Not Changed: No change in study drug dosage was made.
- Drug Withdrawn: The study product was permanently stopped.
- Dose Reduced: The dosage of study product was reduced.
- Drug Interrupted: The study product was temporarily stopped.
- Not Applicable

#### **8.4.6. Other Action Taken for Event**

- None.
  - No treatment was required.
- Medication required.
  - Prescription and/or OTC medication was required to treat the AE.
- Hospitalization or prolongation of hospitalization required.

- Hospitalization was required or prolonged due to the AE, whether or not medication was required.
- Other.

#### **8.4.7. Adverse Event Outcome**

- Recovered/Resolved
  - The subject fully recovered from the AE with no residual effect observed.
- Recovering/Resolving
  - The AE improved but has not fully resolved.
- Recovered/Resolved with Sequelae
  - The residual effects of the AE are still present and observable.
  - Include sequelae/residual effects.
- Not Recovered/Not Resolved
  - The AE itself is still present and observable.
- Fatal
  - Fatal should be used when death is a direct outcome of the AE.
- Unknown

#### **8.5. Serious Adverse Events Reporting-Procedure for Investigators**

All AEs, SAEs and AESIs, and medication errors including overdose will be reported in the eCRF.

Serious events that are also efficacy endpoints (eg, PD) and/or safety endpoints will be exempted from SAE processing and expedited reporting. Disease progression should not be reported as an AE/SAE. However, when a subject dies from PD with no other immediate causes, “disease progression” should be reported as an SAE and captured on designated eCRF. These events are clinically anticipated events in the target treatment population, and will be periodically reviewed by the Daiichi Sankyo safety teams to ensure prompt identification of any clinically concerning safety issues.

The following types of events should be reported by the Investigator in electronic data capture (EDC) within 24 hours of awareness. A treatment-emergent adverse event (TEAE) is defined as an AE that occurs, having been absent before the first dose of study drug, or has worsened in severity or seriousness after the initiating the study drug until 47 days after last dose of the study drug. SAEs with an onset or worsening 48 days or more after the last dose of study drug, if considered related to the study treatment, are also TEAEs.

- SAEs (see Section 8.4.2 for definition)
- All potential ILD cases should be reported within 24 hours; including both serious and non-serious potential ILD cases (potential ILD is defined by the Event Adjudication Site Manual List of PTs).

- Hepatic events (both serious and non-serious) which meet the potential Hy's Law criteria defined as an elevated (ALT or AST)  $\geq 3 \times$  ULN and an elevated TBL  $> 2 \times$  ULN that may occur either at different time points or simultaneously during the study conduct. A targeted questionnaire is in-built within the eCRF to collect relevant additional information for these potential cases.
- Overdose, defined as the accidental or intentional administration of any dose of a product that is considered both excessive and medically important. An "excessive and medically important" overdose includes any overdose in which either a serious adverse event, a non-serious adverse event, or no adverse event occurs and is considered by the Investigator as clinically relevant, i.e. poses an actual or potential risk to the subject.

Overdose is always serious. By definition an overdose is medically important, which meets the seriousness criterion of important medical event. An overdose can occur with or without an AE. AEs can either be serious or non-serious. Details of the overdose including trastuzumab deruxtecan dosage, clinical course, associated AEs, and outcome must be captured in the Narrative form of the CRF within eDC. Disease progression/worsening of primary cancer (gastric, gastroesophageal junction [GEJ] adenocarcinoma, or breast cancer) will not be recorded as an AE on the Adverse Event eCRF. However, events associated with disease progression may be recorded as AEs.

Death due to disease progression should be recorded on the Death eCRF.

All events (serious and non-serious) must be reported with Investigator's assessment of the event's seriousness, severity, and causality to the study drug. A detailed narrative summarizing the course of the event, including its evaluation, treatment, and outcome should be provided. Specific or estimated dates of event onset, treatment, and resolution should be included when available. Medical history, concomitant medications, and laboratory data that are relevant to the event should also be summarized in the narrative. For fatal events, the narrative should state whether an autopsy was or will be performed, and include the results if available. Source documents (including medical reports) will be retained at the study site and should not be submitted to the Sponsor for SAE reporting purposes.

Urgent safety queries must be followed up and addressed promptly. F/U information and response to non-urgent safety queries should be combined for reporting to provide the most complete data possible within each F/U.

Please call the local SAE Hotline (see Study Manual) or your study monitor for any questions on SAE reporting.

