**Safety Endpoints**

- Primary safety endpoints will include serious adverse events (SAEs), treatment-emergent adverse events (TEAEs), and adverse events (AEs) and adverse events of special interest (AESIs) leading to discontinuation.
- Other safety endpoints will include physical examination findings (including ECOG PS), vital sign measurements, standard clinical laboratory parameters, ECG parameters, ECHO or MUGA findings, and ophthalmologic findings. TEAEs will be graded according to the NCI-CTCAE version 4.03.
- ADA against DS-8201a will be assessed as a secondary safety endpoint.

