### **2.3. Study Endpoints**

#### **2.3.1. Primary Endpoints**

Safety endpoints:

- Safety endpoints will include serious adverse events (SAEs), TEAEs, AEs and AESIs leading to discontinuation.
- Other safety endpoints will include physical examination findings (including Eastern Cooperative Oncology Group Performance Status [ECOG PS]), vital sign measurements, standard clinical laboratory parameters, ECG parameters, ECHO or MUGA findings, and ophthalmologic findings. TEAEs will be graded according to the National Cancer Institute Common Terminology Criteria for Adverse Events (NCI-CTCAE) version 4.03.

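### Section 8.5 exempts serious events that are safety endpoints from SAE processing and expedited reporting, yet SAEs are named safety endpoints and the same section wants them reported within 24 hours

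*Combined protocol and SAP*

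**What the plan says.** Section 8.5, the investigators' procedure for SAEs, contains three instructions that bear on each other.

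- Recording: "All AEs, SAEs and AESIs, and medication errors including overdose will be reported in the eCRF".
- Exemption: "Serious events that are also efficacy endpoints (eg, PD) and/or safety endpoints will be exempted from SAE processing and expedited reporting". The sentences that follow deal with disease progression. It is not to be reported as an AE or SAE, except that a death with PD as the only immediate cause is an SAE. The exempt events are described as anticipated in this population and subject to periodic review by the sponsor's safety teams.
- Timing: "The following types of events should be reported by the Investigator in electronic data capture (EDC) within 24 hours of awareness". The first entry on that list is SAEs as defined in Section 8.4.2, with no carve-out for endpoint events. Potential ILD (serious or not), hepatic events meeting potential Hy's Law criteria, and overdose have entries of their own.

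The term safety endpoints is used in several places. Section 2.3.1, under Primary Endpoints, says: "Safety endpoints will include serious adverse events (SAEs), TEAEs, AEs and AESIs leading to discontinuation". Section 8.1, at the head of the chapter that holds the exemption, says: "Safety endpoints will include SAEs, TEAEs, AEs and AESIs leading to discontinuation". The synopsis and Section 11.4.3 also name SAEs as safety endpoints.

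Section 8.2 makes Section 8.5 the governing procedure: "All AEs and SAEs are to be reported according to the procedures in Section 8.5".

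**The concern.** An exemption for endpoint events makes sense where the endpoint is an expected outcome of the disease, such as progression. Here the primary endpoints are adverse events, so extending the exemption to safety endpoints brings in the events that the section exists to have reported. A site that reads Section 8.5 from top to bottom is told that such events are exempt and then that they are due within 24 hours.

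At stake is the prompt handling of serious events in a trial whose primary objective is safety. Sections 11.6 and 15.9 state that there is no data monitoring committee or board. Oversight falls to the safety monitoring team of Section 11.7, which meets regularly, after 6 patients have completed Cycle 1, and when necessary. A reporting rule in that setting should not depend on the reader's guess at what was meant.

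**Working it through.** No arithmetic applies and the plan gives no figure to reproduce. The check sets the texts side by side.

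**1. Literal scope.** Serious events that are safety endpoints are exempt (Section 8.5). SAEs are safety endpoints (synopsis; Sections 2.3.1, 8.1, 11.4.3). Every SAE is therefore exempt. No section lists a smaller set of exempt safety endpoint events.

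**2. Against the duties.** The 24-hour list in Section 8.5 opens with "SAEs (see Section 8.4.2 for definition"), unqualified. Section 8.2 sends all SAEs to Section 8.5, so no other section settles the conflict. Section 8.2 itself excludes only PD and exempts no safety endpoint.

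**3. Possible readings of the exemption.**

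| Reading | Result |
|---|---|
| All safety endpoints, as written | Contradicts the SAE entry on the 24-hour list |
| Progression only | The safety-endpoint phrase does no work, because PD is already covered as an efficacy endpoint |
| Some safety endpoints but not others | The protocol does not say which |
| Investigators enter SAEs in EDC within 24 hours, but the later processing and expediting are waived | Not stated. Section 8.6 promises notification of SUSARs without saying how that fits such a waiver |

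None of the four leaves the sentence sound as it stands.

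**4. Which events depend on the conflicting text.**

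| Event | Own entry on the 24-hour list? |
|---|---|
| Potential ILD, serious or not | Yes |
| Hepatic event meeting potential Hy's Law criteria | Yes |
| Overdose | Yes |
| Serious LVEF decrease | No, general SAE entry only |
| Any other SAE | No, general SAE entry only |

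Section 8.3 names two AESIs, ILD and LVEF decrease. The first is protected by its own entry and the second is not. Section 8.3 adds targeted questionnaires for LVEF-related events but sets no reporting time.

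**5. What the exemption does not touch.** It removes processing and expedited reporting. It does not remove recording. The first sentence of Section 8.5 and the collection rule in Section 8.2 still put every SAE in the eCRF, and the tables of Section 11.4.3.1 can be built from those data.

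**6. Would deleting the safety-endpoint phrase be enough?** The sentence would then exempt serious events that are efficacy endpoints, with PD only as an example. OS is an efficacy endpoint, and PFS counts death from any cause (Section 11.4.1). Read with the same literalness, the shortened sentence would exempt every death, although Section 8.2 says that the cause of a death is always reported as an SAE. The exempt event has to be named.

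**The case against.** The strongest reply is that context settles the meaning. The only example given is PD, the next sentences concern progression, the exempt class is described as clinically anticipated, and Section 8.2 and the later text of Section 8.5 exclude progression alone. A section on how to report SAEs cannot sensibly exempt all of them and then list them for 24-hour reporting. Most experienced sites would report, and Section 8.5 offers an SAE hotline for questions. This stands as evidence of intent, and it limits the likely harm. It does not mend the sentence, since if progression was all that was meant, the phrase about safety endpoints is idle, and if more was meant, the protocol does not say what.

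A reader might go further and infer that sites could hold back urgent reports of serious ILD. The documents do not support that. Potential ILD has a separate 24-hour entry, serious or not, and Section 8.3.1 sends all potential cases to independent adjudication.

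A reader might also infer that the primary endpoint would be incomplete. That is not supported either, because the duty to record SAEs in the eCRF is stated apart from the exemption and is untouched by it.

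**Conclusion.** Wrong as written: Section 8.5 contradicts itself, and its exemption contradicts the protocol's own definition of safety endpoints. The literal scope is every SAE. The scope in real doubt is the expedited handling of serious events that rely on the general SAE entry alone, with serious LVEF decrease the clearest case. No number of affected reports can be derived from the documents, and no sample size, estimate or planned table changes.

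The conclusion assumes that safety endpoints in Section 8.5 means what it means in Sections 2.3.1 and 8.1, since no other meaning is given. It does not assume that sites would in fact withhold reports. The sentence should be corrected because it is an operative safety instruction and the correction costs almost nothing.

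**What to change.** Amend the exemption sentence in Section 8.5 in three respects:

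1. Delete the words *and/or safety endpoints*.
2. Replace the open-ended reference to efficacy endpoints with an express statement that disease progression is the only exempt event.
3. Keep the existing rule that a death with PD as its only immediate cause is reported as an SAE, and say that all other serious events, including other deaths, follow the 24-hour list.

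Suggested wording: *Disease progression is the only event exempt from SAE processing and expedited reporting. A death for which progression is the sole immediate cause is still reported as an SAE. Every other serious event is reported as listed below.*

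Then check the new sentence against the progression and death rules in Section 8.2 and against the 24-hour list, and make clear that the periodic review by the safety teams refers to progression.

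The cost is one reworded sentence in an amendment and a note to sites. There is no effect on sample size, visit schedule, data collection or analysis.
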